### **12.3 Planned Interim Analyses (if applicable)**

Not applicable.

### **12.4 Final Analysis Plan**

#### **Analysis of Primary Endpoints**

The relationship between AXL expression as a continuous variable with clinical response will be analyzed using the Wilcoxon rank sum test.

#### **Analysis of Secondary Endpoints**

The safety of pre-operative cetuximab, as evaluated by hospital re-admissions for wound care or surgical complications attributed to cetuximab within 28 days after surgery, will be reported as a proportion including an exact 95% confidence interval.

#### **Analysis of Correlative Endpoints**

Summary statistics of the change in Ki67 ( $\Delta$ Ki67), as established by the surgical specimen, will be reported for the response to cetuximab endpoint. Correlation between  $\Delta$ Ki67 and putative biomarkers will be analyzed as a continuous variable and will be tested using Pearson's correlation coefficient. Correlation between two biomarkers such as AXL and HER3 expression as continuous variables will be investigated using Pearson's correlation coefficient.

Summary statistics will be used to report circulating tumor cells at each time point and the changes between time points. The association of change in circulating tumor cells with  $\Delta$ Ki67 (early response) will be explored graphically and with Pearson's correlation coefficient.

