### **3.2.3 Exploratory Endpoints**

- 3.2.3.1 Change in Ki67 from pre- versus post-cetuximab treated tumors and its correlation with levels of AXL expression pre-cetuximab treatment
- 3.2.3.2 Correlation of measures of putative markers of cetuximab sensitivity, including protein, RNA, circulating tumor cells with cetuximab response, measured by Ki67
- 3.2.3.3 Establishment of patient-derived xenografts with known sensitivity/resistance to cetuximab

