### **Determination of putative biomarkers of CTX sensitivity**

The biologic correlate study team will formalin fix and paraffin embed (FFPE) approximately one third of the research biopsy tissue to be used to assess putative biomarkers of CTX sensitivity (e.g. total and phosphorylated AXL, EGFR and HER3 expression using immunohistochemistry assays). The FFPE research and surgical specimens will be used to establish the change in Ki67 ( $\Delta$ Ki67).

Correlations between the change in Ki67 index ( $\Delta$ Ki67) and AXL expression and HER3 expression in the research biopsy will be performed. Further correlation between other biomarkers and AXL expression will be performed.

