### 12.2 Sample Size Considerations

We plan to enroll 36 HNSCC patients, powered on the basis of the primary study endpoint: the clinical response rate to cetuximab according to RECIST criteria in low AXL vs. high AXL patients (measured using VECTRA/inForm software). Previous data show that 1 in 3 patients respond to cetuximab, and about one-third (21/57 or 37%) of HNSCC patients have high AXL expression. This sample size is based on 90% power to detect a difference between a response rate of 20% in the high AXL (2+ or 3+) group vs. 65% in the low AXL (0 or 1) group, with an expected ratio of 2:1 low vs. high AXL expression participants. One-sided type I error was fixed at 5%.

For evaluation of safety endpoints, any participant that undergoes a research biopsy will be included. For evaluation of efficacy, molecular/correlative studies, and creation of PDXs, participants must receive both cetuximab doses in their

entirety and have surgical resection of the tumor. If a participant is unevaluable for these endpoints, then the patient will be replaced at the discretion of the principal investigator.

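### Change in Ki67 is tested against AXL and other markers without baseline Ki67; a baseline-adjusted analysis should be pre-specified beside the Pearson correlation

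*Combined protocol and SAP*

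**What the plan says.** The first correlative objective (Section 3.1) relates AXL to the change in Ki67. Section 3.2.3 lists it as an exploratory endpoint: "Change in Ki67 from pre- versus post-cetuximab treated tumors and its correlation with levels of AXL expression pre-cetuximab treatment". Section 8.2.3 takes the change from the research biopsy and the surgical specimen, and says that correlations between this change "and AXL expression and HER3 expression in the research biopsy will be performed". Section 12.4 (Analysis of Correlative Endpoints) gives the only test: the correlation of the change with "putative biomarkers will be analyzed as a continuous variable and will be tested using Pearson's correlation coefficient". The change in circulating tumour cells is related to the change in Ki67 in the same way.

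No section adjusts for baseline Ki67, although the study schematic has the research biopsy scored for it. No section says whether the change is a difference, a percentage or a ratio. The documents give no Ki67 mean, SD, expected fall, pre/post correlation or AXL–baseline Ki67 correlation. The sample size concerns clinical response only: "We plan to enroll 36 HNSCC patients, powered on the basis of the primary study endpoint" (Section 12.2).

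**The concern.** A post-minus-pre difference contains the baseline value. Unless post-treatment Ki67 rises one-for-one with baseline, the difference is correlated with baseline, for two reasons: a proportional fall is larger in absolute terms where baseline is high, and biopsy sampling error adds regression to the mean. This has two consequences.

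- **Power.** Baseline variation stays in the change score as noise, even when the marker has nothing to do with baseline.
- **Bias.** If the marker correlates with baseline Ki67, that correlation carries over into the marker–change correlation. AXL and baseline Ki67 come from the same biopsy. Section 2 (Mechanisms of resistance) reports AXL associated with higher pathologic grade, so a positive correlation with a proliferation marker is plausible, but that is an inference without a figure. In that direction high-AXL tumours would show larger falls and look more sensitive, which works against the trial's own hypothesis.

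Section 2 also names the change in Ki67, beside tumour dimensions, as a measure of response to cetuximab. A misleading AXL–Ki67 result would therefore colour the reading of the main question.

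**Working it through.** **The plan's own figure.** There is none for Ki67. The sample size can be reproduced, which shows that it does not depend on Ki67. Section 12.2 gives "response rate of 20% in the high AXL (2+ or 3+) group vs. 65% in the low AXL (0 or 1) group". It also assumes two low-AXL patients for each high-AXL patient, 90% power and one-sided 5%. With the unpooled normal approximation:

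n(high) = (1.645 + 1.282)² × (0.20×0.80 + 0.65×0.35/2) / 0.45² = 8.564 × 0.27375 / 0.2025 = 11.58, rounded to 12. The total is 12 + 24 = 36, with power 90.9%.

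**Model for the Ki67 analysis (all inputs assumed).** n = 36; baseline Ki67 B with mean 40 and SD 15; post-treatment Ki67 = s·B + β·A + e, up to a constant, with residual SD 10. A is AXL in SD units, with correlation a to B. s = 0.5 is a 50% fall, s = 0.7 a 30% fall. β = 0 or 5 points per SD of AXL. Tests are two-sided at 5%. The change is D = (s−1)B + βA + e. Approximate power is Φ(z − 1.96) + Φ(−z − 1.96), with z = atanh(r)·√33 for the change score and atanh(partial r)·√32 for the adjusted test.

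**Step 1: power when AXL is unrelated to baseline (a = 0, β = 5).** r = 5/√[(1−s)²·225 + 25 + 100].
- s = 0.5: 5/√181.25 = 0.371, power about 61%.
- s = 0.7: 5/√145.25 = 0.415, power about 72%.
- s = 1: 5/√125 = 0.447, power about 79%.
- Adjusted, any s: partial r = 5/√125 = 0.447, power about 78%.

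**Step 2: false positives when a = 0.3 and β = 0.** r = −(1−s)·15·0.3/√[(1−s)²·225 + 100].
- s = 0.5: −2.25/√156.25 = −0.18, rejection about 18%.
- s = 0.7: −1.35/√120.25 = −0.123, rejection about 11%.

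**Step 3: a true effect masked (a = 0.3, β = 5, s = 0.5).** r = (5 − 2.25)/√(56.25 + 25 − 22.5 + 100) = 2.75/√158.75 = 0.218, power about 25%. Adjusted: partial r = 5·√0.91/√(25·0.91 + 100) = 0.431, power about 74%.

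**Step 4: simulation of the same settings (20,000 trials each).**

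| Slope s | a | AXL effect | Change score | Adjusted |
|---|---|---|---|---|
| 0.5 | 0 | 5 points/SD | 62% | 79% |
| 0.7 | 0 | 5 points/SD | 73% | 79% |
| 1.0 | 0 | 5 points/SD | 80% | 79% |
| 0.5 | 0.3 | none | 18% | 5% |
| 0.7 | 0.3 | none | 11% | 5% |
| 0.5 | 0.3 | 5 points/SD | 25% | 75% |
| 0.5 | −0.3 | 5 points/SD | 90% | 75% |

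In the last row the surplus of the change score is bias, not valid power. With a = 0 and no AXL effect both tests reject 5%.

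**Step 5: a second parameterisation.** With equal pre and post SDs, pre/post correlation 0.3 to 0.7 and no AXL effect, the change score rejects 18% down to 10% at a = 0.3 and 43% down to 20% at a = 0.5; the adjusted test stays at about 5%. At a = 0 the residual variance ratio, adjusted to change, is (1 + r)/2 = 0.65 to 0.85.

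**Step 6: noisy baseline.** Steps 1 to 5 treat baseline Ki67 as error-free. With reliability 0.5 to 0.7, a = 0.3, s from 0.5 to 1 and no AXL effect, the adjusted test rejects about 6–15%. At s = 1 the change score stays at 5%. At reliability 0.5 and a 30% fall the change score also does better (7% against 9% or more).

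**Step 7: relative change.** With a 50% fall and a = 0.3, the null rejection rate is 18% for the absolute difference, but about 7% for percent change and 5.5% for the log ratio.

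**The case against.** The strongest reply has four parts.

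1. **The definition of change is open.** A reader might infer that the plan uses the raw difference. The documents do not say so. Step 7 shows that under a proportional fall a relative change removes most of the bias. This stands: the bias and power figures above are conditional on an absolute change, and the missing definition is itself a gap.

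2. **Adjustment is not uniformly better.** A reader might infer that the Pearson analysis should be dropped because the adjusted test holds 5%. It does so only with an error-free baseline. AXL is an observed tumour characteristic in a single-arm study, not a randomised factor, so change score and adjustment answer different questions and neither is always unbiased (Step 6). This stands, and it rules out simple replacement.

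3. **The inputs are assumed.** Creating or hiding an association needs a non-zero AXL–baseline correlation, and the power gain disappears when the slope is near 1. This stands. The power loss at a = 0 needs no AXL–baseline correlation, but it does need a slope away from 1.

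4. **The analysis is exploratory, and baseline Ki67 is collected, so adjustment can be added at reporting.** True, and it limits the severity. But an adjusted result added after the unadjusted one has been seen is open to selective choice. Naming it beforehand costs almost nothing.

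**Conclusion.** The point holds in a limited form. The plan's only test of Ki67 change against AXL ignores a baseline covariate that is already measured. For an absolute change at n = 36, under the assumed SDs and effect, this costs about 17 points of power with a 50% fall (79 − 62), about 6 with a 30% fall (79 − 73), and none at slope 1, when AXL is unrelated to baseline. With an assumed AXL–baseline correlation of 0.3, false positives are 11–18% rather than 5%, and under a 50% fall power for a real effect can drop from 75% to 25%.

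It would go too far to read 11–18% as this trial's error rate: the Ki67 mean, SDs, size of fall, effect size and AXL–baseline correlation are all assumptions. Nor does the point reach the main result. The primary analysis is a Wilcoxon test of AXL against clinical response and does not use Ki67, and N=36 rests on response rates alone. The importance is low to moderate: a worthwhile correction to an exploratory analysis.

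**What to change.** In Section 12.4, Analysis of Correlative Endpoints:

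- Pre-specify linear regression of post-treatment Ki67 on each marker (AXL, HER3, other markers, change in circulating tumour cells) with baseline Ki67 as covariate. Report the adjusted slope with its confidence interval.
- Keep the Pearson correlation with the change in Ki67 as a sensitivity analysis and report both. If they disagree, discuss measurement error in the biopsy Ki67 as one explanation.
- State whether the change is absolute or relative, here and in Sections 3.2.3 and 8.2.3.

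Cost: wording and one degree of freedom. No new samples, visits or patients are needed. The remaining weakness is that the adjusted test is not fully unbiased with a noisy baseline (about 6–15% null rejection at reliability 0.5–0.7 and correlation 0.3), which is why the change-score analysis stays.

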## **13 SOURCE DOCUMENTS AND ACCESS TO SOURCE DATA/DOCUMENTS**

Study staff will maintain appropriate medical and research records for this study, in compliance with ICH E6, Section 4.9 and regulatory and institutional requirements for the protection of confidentiality of subjects. Study staff will permit authorized representatives of NIDCR and regulatory agencies to examine (and when required by applicable law, to copy) research records for the purposes of quality assurance reviews, audits, and evaluation of the study safety, progress and data validity.

Source documents will include all records within the HealthLink Electronic Medical Records system such as hospital records, clinical and office charts, laboratory notes, memoranda, pharmacy dispensing records, copies or transcriptions certified after verification as being accurate and complete, photographs or digital photo files, x-rays, and subject files and records kept at the pharmacy, at the laboratories, and medico-technical departments involved in the clinical trial. In addition, protocol specific forms will be designed which require treating physician signature to serve as source documents. This may include forms such as toxicity forms with grading and attribution and tumor measurement forms.

## **14 QUALITY CONTROL AND QUALITY ASSURANCE**

### **14.1 Monitoring, Auditing, and Data Quality Control and Assurance Measures by Study Team.**

All personnel involved in FDA regulated clinical trial activities are required to complete the Human Subjects Training and Good Clinical Practice (GCP) via CITI every 3 years. Training is monitored at each IRB continuing review and with the submission of protocol amendments.

At the protocol level, the Principal Investigators will assign and document protocol responsibilities based on study roles. Training on all IRB approved protocols (initial version and subsequent amendments) are documented for each person listed as key personnel on the University of Wisconsin Health Sciences IRB application. These documents are retained with the study regulatory files, and collection is coordinated by Human Oncology regulatory staff.

Eligibility checklists are signed by the study coordinator and the treating physician prior to enrollment. Adverse event grading and attributions are assigned by physicians at clinic visits and will be signed by the physician at that time.

A data report will be run quarterly to ensure study data is entered into the study database in a timely manner. After the report is run, the Research Program Manager will review and audit at least 25% of accrued cases since the last report was run. Auditing assistance will be provided by a study coordinator not involved in the cases being audited. Audits will include case review (Informed consent, eligibility, response, toxicity) and source document review.

Other relevant UWCCC SOPs that would be followed include:

- Adverse Event Assessment and Documentation\_SOP
- CTRP and ClinicalTrials.gov Reporting\_SOP
- Delegation of Authority Log\_SOP

- DSMS Reporting Guidelines\_SOP
- Informed Consent Process\_SOP
- Maintaining a Regulatory File\_SOP
- OnCore Data Quality Assurance\_SOP
- Protocol Deviation\_Guidance
- Reportable Events\_SOP
- Reporting of Serious Adverse Events (SAEs) at UWCCC, 1SP, JC, And Affiliate Sites\_SOP
- Source Documentation\_SOP
- Study Close Out\_SOP

## 15 ETHICS/PROTECTION OF HUMAN SUBJECTS

### 15.1 Ethical Standard

The investigator will ensure that this study is conducted in full conformity with the principles set forth in The Belmont Report: Ethical Principles and Guidelines for the Protection of Human Subjects of Research, as drafted by the US National Commission for the Protection of Human Subjects of Biomedical and Behavioral Research (April 18, 1979) and codified in 45 CFR Part 46 and/or the ICH E6.

### 15.2 Institutional Review Board

The protocol, informed consent form(s), recruitment materials, and all subject materials will be submitted to the IRB for review and approval. Approval of both the protocol and the consent form must be obtained before any subject is enrolled. Any amendment to the protocol will require review and approval by the IRB before the changes are implemented in the study.

### 15.3 Informed Consent Process

Informed consent is a process that is initiated prior to the individual agreeing to participate in the study and continues throughout study participation. Extensive discussion of risks and possible benefits of study participation will be provided to subjects and their families, if applicable. A consent form describing in detail the study procedures and risks will be given to the subject. Persons who are not fluent in English and persons with impaired decision-making capacities will not be eligible for enrollment in this study.

Consent forms will be IRB-approved, and the subject is required to read and review the document or have the document read to him or her. The investigator

or designee will explain the research study to the subject and answer any questions that may arise. The subject will sign the informed consent document prior to any study-related assessments or procedures. Subjects will be given the opportunity to discuss the study with their surrogates or think about it prior to agreeing to participate. They may withdraw consent at any time throughout the course of the study. A copy of the signed informed consent document will be given to subjects for their records. The rights and welfare of the subjects will be protected by emphasizing to them that the quality of their clinical care will not be adversely affected if they decline to participate in this study.

The consent process will be documented in the clinical or research record.

#### **15.4 Exclusion of Women, Minorities, and Children (Special Populations)**

Children are excluded from this study because insufficient data are available in adults to judge potential risks in children.

Individuals of any gender or racial/ethnic group may participate in this study.

#### **15.5 Subject Confidentiality**

Subject confidentiality is strictly held in trust by the investigators, study staff, and the sponsor(s) and their agents. This confidentiality is extended to cover testing of biological samples and genetic tests in addition to any study information relating to subjects.

All members of the study team will be listed on the IRB application and are required to undergo annual HIPAA training to ensure responsible conduct regarding protected health information (PHI) in research. In addition, Human Subjects Training and Good Clinical Practice trainings are required every three years for members of the study team.

The study protocol, documentation, data, and all other information generated will be held in strict confidence. No information concerning the study or the data will be released to any unauthorized third party without prior written approval of the sponsor. All PHI is stored securely on password protected servers.

The study monitor or other authorized representatives of the sponsor may inspect all study documents and records required to be maintained by the investigator, including but not limited to, medical records (office, clinic, or hospital) for the study subjects. The clinical study site will permit access to such records.

To further protect the privacy of study participants, the Secretary, Health and Human Services (HHS), has issued a Certificate of Confidentiality (CoC) to all

researchers engaged in biomedical, behavioral, clinical, or other human subjects research funded wholly or in part by the federal government. Recipients of NIH funding for human subjects research are required to protect identifiable research information from forced disclosure per the terms of the NIH Policy (<https://humansubjects.nih.gov/coc/index>). As set forth in 45 CFR Part 75.303(a) and NIHGPS Chapter 8.3, recipients conducting NIH-supported research covered by this Policy are required to establish and maintain effective internal controls (e.g., policies and procedures) that provide reasonable assurance that the award is managed in compliance with Federal statutes, regulations, and the terms and conditions of award. It is the NIH policy that investigators and others who have access to research records will not disclose identifying information except when the participant consents or in certain instances when federal, state, or local law or regulation requires disclosure. NIH expects investigators to inform research participants of the protections and the limits to protections provided by a Certificate issued by this Policy.

## **15.6 Future Use of Stored Specimens and Other Identifiable Data**

Residual samples will be relinquished to the TSB Biobank (2016-0934) for future exploratory analyses at the termination of this study. All subjects will have already signed a consent for the TSB Biobank protocol as part of the inclusion criteria.

Any use of specimens outside the context of this protocol, including genetic testing, will only occur after IRB approval.

## **16 DATA HANDLING AND RECORD KEEPING**

This study will report clinical data using the UWCCC data management system utilizing study specific case report forms. Key study personnel are trained on the use of case report forms and will comply with protocol specific instructions for data collection.

Patient demographics, patient specific study treatment calendars, adverse events and other information will be maintained with the UWCCC data management system.

Participant data will be collected using protocol specific case report forms (CRFs). The CRFs will be approved by the study's Principal Investigator and the study biostatistician prior to release for use. The Study Coordinator or designee will be responsible for registering the patient into the UWCCC data management system at time of study entry, completing CRFs based on the patient specific calendar, and updating the patient record until patient death or end of required study participation.

## **16.1 Data Management Responsibilities**

Data collection and accurate documentation are the responsibility of the study staff under the supervision of the investigator. All source documents and laboratory reports must be reviewed by the study team and data entry staff, who will ensure that they are accurate and complete. Unanticipated problems and adverse events must be reviewed by the investigator or designee.

UWCCC Radiotherapy will serve as the Clinical Research Office for this trial.

## **16.2 Data Capture Methods**

Data will be collected through the web-based clinical research platform, OnCore (Forte Research), a system compliant with Good Clinical Practices and Federal Rules and Regulations. UWCCC personnel will coordinate and manage data for quality control assurance and integrity. All data will be collected and entered into OnCore by study site personnel.

## **16.3 Types of Data**

Patient demographics, patient medical history, patient specific study treatment calendars, adverse events, laboratory/pathology reports obtained during the course of treatment and afterwards, e.g., blood tests, biopsy results), findings from physical exams, and imaging scan reports/outcomes will be maintained with the UWCCC data management system.

